13 RECORDING AND REPORTING OF EVENTS AND INCIDENTS

13.1 Definitions of Adverse Events

This is an observational study, there are no interventions, and we do not anticipate any adverse events associated with this project. We will however, use the standard definitions of adverse events as supplied by the UCL JRO.

Term	Definition
Adverse Event (AE)	Any untoward medical occurrence in a patient or study participant, which does not necessarily have a causal relationship with the procedure involved.
Serious Adverse Event (SAE).	Any adverse event that: 
• results in death,• is life-threatening*,• requires hospitalisation or prolongation of existing hospitalisation**,• results in persistent or significant disability or incapacity, or• consists of a congenital anomaly or birth defect

*A life- threatening event, this refers to an event in which the participant was at risk of death at the time of the event; it does not refer to an event which hypothetically might have caused death if it were more severe.

** Hospitalisation is defined as an in-patient admission, regardless of length of stay. Hospitalisation for pre-existing conditions, including elective procedures do not constitute an SAE.

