The study builds on the previous research of the CI and the Marie Curie Palliative Care Research Department (MCPCRD), within UCL's Division of Psychiatry where the study will take place. In 2013, the MCPCRD systematically reviewed the prevalence and predictors of grief before and after the death in carers of people with dementia.[3] Our analysis of primary care data found that carers of people with dementia used more psychotropic drugs prior to bereavement than other carers.[18] Mentor [name] and supervisor [name] reviewed evidence on advance care planning (ACP) in dementia and found considerable barriers to implementing ACP in practice. They found that carers' capacity to make best interest decisions about end of life is influenced by religious beliefs, education, guilt and burden.[19] Their qualitative work identified that even in mild stages, people with dementia have difficulty envisaging themselves being more dependent on others.[14] The 3-year Compassion study, led by [name] and [name] (National Institute for Health Research [NIHR] portfolio ref. CRN-PCRN 12621; 12623) [20], involved a small cohort study of people with advanced dementia and their family carers. We found that 26% of carers reported depression, 41% anxiety and grief before death was high. Carers were offered minimal emotional support before and after their relative's death [21]. We developed the Compassion Intervention to promote integrated palliative

dementia care.[22, 23] This was tested in two care homes where the CI was employed as an Interdisciplinary Care Leader. Few carers were aware of common end of life symptoms.[24] The importance of studying grief and end of life support for carers of people with dementia was strongly endorsed by carers of the Alzheimer's Society Research Network whom the CI consulted in a specially convened focus group. Network members expressed major concerns in the current provision of end of life preparation and information as well as grief support, reinforcing this as a neglected topic requiring more research and development.

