13.2 Assessments of Adverse Events

In the unlikely event that this occurs, each adverse event will be assessed for severity, causality, seriousness and expectedness as described below.

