13.6 Recording adverse events

[figure not shown]
In the unlikely occurrence of an adverse events this will be will be recorded in the CRF.

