13.7 Procedures for recording and reporting Serious Adverse Events

All serious adverse events will be reported to the CI and recorded in the CRF, and the sponsor's AE log.

All SAEs (except those specified in section 16.5 as not requiring reporting to the Sponsor) must be recorded on a serious adverse event (SAE) form. The CI will complete an SAE form and the form will be emailed to [contact] within 5 working days of becoming aware of the event. The CI will respond to any SAE queries raised by the sponsor as soon as possible. Where the event is unexpected and thought to be related to the procedure this must be reported by the Investigator to the Health Research Authority within 15 days.

Flow Chart for SAE reporting

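### The SAE footnote in section 13.1 excludes every admission for a pre-existing condition, so an unplanned admission for worsened depression or anxiety could bypass the SAE route to the sponsor and the HRA

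*Combined protocol and SAP*

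**What the plan says.** Section 13.1 adopts the sponsor's standard definitions. An adverse event (AE) is "Any untoward medical occurrence in a patient or study participant, which does not necessarily have a causal relationship with the procedure involved". An AE is serious if it meets one of five criteria. One is that it "requires hospitalisation or prolongation of existing hospitalisation". A footnote to that criterion defines hospitalisation as any in-patient stay and ends: "Hospitalisation for pre-existing conditions, including elective procedures do not constitute an SAE". The other criteria (death, threat to life, congenital anomaly, and an event that "results in persistent or significant disability or incapacity, or") carry no exclusion for pre-existing conditions.

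Under section 13.2, "each adverse event will be assessed for severity, causality, seriousness and expectedness as described below". Section 13.6 sends AEs to the CRF and names no onward report. Section 13.7 applies to SAEs: they also go into the sponsor's AE log, and the chief investigator sends an SAE form within 5 working days. An event that is both unexpected and thought related "must be reported by the Investigator to the Health Research Authority within 15 days". That sentence stands inside the SAE procedure. Section 13.7 also exempts from sponsor reporting any SAEs listed in a section 16.5.

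**The concern.** Section 12.1 expects that an interview on loss, grief and end-of-life care may upset participants. One plausible serious form of that harm is a worsening of depression or anxiety the carer already had. The footnote removes an admission for exactly that from the hospitalisation criterion. Elective procedures are given as one example of what is excluded, so they do not limit the exclusion to planned care. The term pre-existing condition is not defined. The Hospital Anxiety and Depression Scale is collected at interview (section 4.1), so the CRF itself may show that symptoms were already present, which makes the label easy to apply.

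At stake is how a rare but important event is classified. An admission could be judged related to the interview under section 13.4 and still never generate an SAE form.

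**Working it through.** The point concerns a definition. The plan gives no figure to reproduce for it, so the check is a side-by-side reading plus one simple count.

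**Path of one event.** Take a carer with depression before the interview who worsens afterwards and has an unplanned admission.

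1. Is it an AE? Yes. The AE definition in 13.1 has no exclusion for pre-existing conditions and needs no causal link.
2. Does it meet the hospitalisation criterion? Not on the literal wording. The footnote has no exception for worsening, urgency or relation to the interview.
3. Does it meet another SAE criterion? Only if it is also fatal, life-threatening or lastingly disabling. If so, it is an SAE despite the footnote, which is attached to the hospitalisation criterion alone.
4. If not, where does it go? It is assessed under 13.2, but the seriousness test is the one in 13.1 and returns not serious. It is entered in the CRF under 13.6.
5. What is missed? The sponsor's AE log, the SAE form within 5 working days and, because of where the sentence stands, the 15-day HRA report, which would in any case need the event to be both unexpected and related.

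**How many carers could be in this position.** Section 5.2 excludes only on language and capacity, so depressed or anxious carers are eligible. Inputs: target sample 150 (section 7.1). For prevalence, section 2 says of an earlier cohort: "We found that 26% of carers reported depression, 41% anxiety and grief before death was high". Expected count = 150 × prevalence. The overlap of the two conditions is not given, so the count with either lies between 150 × the larger rate and 150 × the sum of the rates.

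| Rates | Depression | Anxiety | Either |
|---|---|---|---|
| As cited | 150 × 0.26 = 39 | 150 × 0.41 = 61.5 | 61.5 to 150 × 0.67 = 100.5 |
| Half as high (assumption) | 150 × 0.13 = 19.5 | 150 × 0.205 = 30.75 | 30.75 to 150 × 0.335 = 50.25 |

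The half-rate row is an assumption that allows for a milder case mix: the cited cohort was small and concerned advanced dementia, while this study takes all stages. These are counts of carers with reported symptoms. The documents give no admission rate, so the number of admissions affected cannot be computed.

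**The exemption in 13.7.** Section 16 is the intellectual property statement and has no subsections. The SAEs exempted from sponsor reporting are therefore not identified anywhere.

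**The case against.** **Stronger readings that the documents do not support.** A reader might infer that such an admission could never be an SAE and would not be recorded at all. That goes too far. Three SAE criteria that could apply to a carer (death, threat to life, lasting disability) are untouched by the footnote, and the event remains an AE, assessed and entered in the CRF. The Trust incident system in section 13.9 may also catch it, although its reach to carers recruited through Join Dementia Research or non-NHS services is unclear.

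A reader might also infer that a report of no SAEs would leave the study with no information on this harm. Section 12.1 shows otherwise. Participants are asked at the end of the interview whether it distressed them, they are called two days later, and the protocol is to be revised if distress exceeds that in the cited bereaved-carer study.

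Nor do the counts of 39 and 62 show how many carers the footnote would exempt. Reported depression is not the same as a documented pre-existing condition.

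**The case for leaving the text alone.** The wording is the sponsor's standard text, used in an observational study that expects no AEs. A worsening could be seen as a new untoward event, with the footnote covering only the condition as it stood before. With a single scheduled follow-up call, a later admission may never become known under any definition.

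**What stands.** Standard text can fit poorly where the named risk is psychological. The narrower reading is sensible, but the footnote does not say it. The ascertainment point is fair: it limits what the change can gain, but gives no reason to misclassify an admission that does become known.

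**Conclusion.** The concern holds in a limited form. Taken literally, section 13.1 removes all admissions for pre-existing conditions from the hospitalisation criterion. An admission for worsened depression or anxiety that meets no other SAE criterion would be an AE in the CRF only, outside the SAE route to the sponsor and the HRA.

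The carers concerned are probably not rare, even at half the cited rates, but that rests on reported symptoms in a small cohort with more advanced dementia and is indicative only. Affected admissions are probably very few. The conclusion assumes that the footnote is applied as written and that the study team learns of the admission. No estimate, test or sample size is affected. This is a safety-reporting gap worth closing because closing it is cheap.

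**What to change.** In section 13.1, limit the exclusion to admissions that were planned or elective before the interview, for a pre-existing condition that has not worsened since. State that an unplanned admission for a worsened pre-existing condition, mental health included, counts as an SAE and follows section 13.7.

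In the same edit, correct the exemption in 13.7 that refers to section 16.5: either point it to the intended list or delete it. Otherwise, sending these events to 13.7 does not secure a report.

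Cost: one or two sentences in 13.1 and a corrected cross-reference in 13.7. The downside is a few more SAE forms, some of them for unrelated chronic illness.

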13.2 Assessments of Adverse Events

In the unlikely event that this occurs, each adverse event will be assessed for severity, causality, seriousness and expectedness as described below.

13.3 Severity

Category	Definition
Mild	The adverse event does not interfere with the participant's daily routine, and does not require further procedure; it causes slight discomfort
Moderate	The adverse event interferes with some aspects of the participant's routine, or requires further procedure, but is not damaging to health; it causes moderate discomfort
Severe	The adverse event results in alteration, discomfort or disability which is clearly damaging to health

13.4 Causality

The assessment of relationship of adverse events to the procedure is a clinical decision based on all available information at the time of the completion of the case report form. As above we do not anticipate any adverse events will arise from this project.

However, if necessary the following categories will be used after review by the CI to define the causality of the adverse event:

Category	Definition
Definitely:	There is clear evidence to suggest a causal relationship, and other possible contributing factors can be ruled out.
Probably:	There is evidence to suggest a causal relationship, and the influence of other factors is unlikely
Possibly	There is some evidence to suggest a causal relationship (e.g. the event occurred within a reasonable time after administration of the study procedure). However, the influence of other factors may have contributed to the event (e.g. the participant's clinical condition, other concomitant events).
Unlikely	There is little evidence to suggest there is a causal relationship (e.g. the event did not occur within a reasonable time after administration of the study procedure).

	There is another reasonable explanation for the event (e.g. the participant's clinical condition).
Not related	There is no evidence of any causal relationship.
Not Assessable	Unable to assess on information available.

13.5 Expectedness

Category	Definition
Expected	An adverse event which is consistent with the information provided in the Participant Information Sheet or clearly defined in this protocol .
Unexpected	An adverse event which is not consistent with the information provided in the Participant Information Sheet or clearly defined in this protocol .

13.6 Recording adverse events

[figure not shown]
In the unlikely occurrence of an adverse events this will be will be recorded in the CRF.

13.7 Procedures for recording and reporting Serious Adverse Events

All serious adverse events will be reported to the CI and recorded in the CRF, and the sponsor's AE log.

All SAEs (except those specified in section 16.5 as not requiring reporting to the Sponsor) must be recorded on a serious adverse event (SAE) form. The CI will complete an SAE form and the form will be emailed to [contact] within 5 working days of becoming aware of the event. The CI will respond to any SAE queries raised by the sponsor as soon as possible. Where the event is unexpected and thought to be related to the procedure this must be reported by the Investigator to the Health Research Authority within 15 days.

Flow Chart for SAE reporting

13.8 Protocol deviations and notification of protocol violations

A deviation is usually an unintended departure from the expected conduct of the study protocol/SOPs, which does not need to be reported to the sponsor. The CI will monitor protocol deviations.

A protocol violation is a breach which is likely to effect to a significant degree –

- (a) the safety or physical or mental integrity of the participants of the study; or
- (b) the scientific value of the study.

The CI and sponsor will be notified immediately of any case where the above definition applies during the study conduct phase.

13.9 Trust incidents and near misses

An incident or near miss is any unintended or unexpected event that could have or did lead to harm, loss or damage that contains one or more of the following components:

- a) It is an accident or other incident which results in injury or ill health.
- b) It is contrary to specified or expected standard of patient care or service.
- c) It places patients, staff members, visitors, contractors or members of the public at unnecessary risk.
- d) It puts the Trust in an adverse position with potential loss of reputation.
- e) It puts Trust property or assets in an adverse position or at risk.

[figure not shown]
Incidents and near misses must be reported to the Trust through DATIX as soon as the individual becomes aware of them.

A reportable incident is any unintended or unexpected event that could have or did lead to harm, loss or damage that contains one or more of the following components:

- a) It is an accident or other incident which results in injury or ill health.
- b) It is contrary to specified or expected standard of patient care or service.
- c) It places patients, staff members, visitors, contractors or members of the public at unnecessary risk.
- d) It puts the Trust in an adverse position with potential loss of reputation.
- e) It puts Trust property or assets in an adverse position or at risk of loss or damage.

14 MONITORING AND AUDITING

The CI will ensure there are adequate quality and number of monitoring activities conducted by the study team. This will include adherence to the protocol, procedures for consenting and ensure adequate data quality. The CI will inform the sponsor should she have concerns which have arisen from monitoring activities, and/or if there are problems with oversight/monitoring procedures. The study Governance Framework provides a clear framework for governance of the study including a data monitoring and research ethics group as shown in the governance structure below.

15 TRAINING

The CI will review and provide assurances of the training and experience of all staff working on this study. Appropriate training records will be maintained in the study files. The CI will complete UCL core training requirements supervising staff as well as statistical courses on regression and statistics for health research (statistics will also be overseen by the study's statistician [name]). Other compulsory training for researchers involved in the study will include Good Clinical Practice and SLMS Information Governance annual training.

Interviews will be undertaken by the CI and the Research Assistant who will be employed. The CI has a psychology and social science background and extensive research experience in undertaking interviews with carers of people with dementia across all stages of dementia progression. The Research Assistant will be employed at a level 6B and will have research experience and a degree relevant to mental health and dementia care. The Research Assistant will be provided with training

from the CI to conduct the interviews. The Research Assistant will observe the CI complete 1-2 interviews. When they feel confident to complete the interview they will complete the interview under observation from the CI. It is envisaged that they will be observed for 2-3 interviews until they feel confident and the CI feels they have achieved the level of competency required for completing the interviews. This training process will also involve debriefing sessions and reflection on the topic and nature of the interviews. After the initial training period, the research assistant will also have regular debriefing sessions with the CI as well as any additional sessions if the research assistant feels they need it. They will ring or meet with the CI directly after any interviews they have found distressing.

Additional clinical support to the CI and Research Assistant will be provided by the fellowship supervisor [name] and co-supervisor [name], both experienced, internationally renowned dementia and end of life care researchers and Old Age Psychiatrists.

16 INTELLECTUAL PROPERTY

We do not anticipate that this study will generate any intellectual property.

17 INDEMNITY ARRANGEMENTS

University College London holds insurance against claims from participants for harm caused by their participation in this clinical study. Participants may be able to claim compensation if they can prove that UCL has been negligent.

18 ARCHIVING

UCL and each participating site recognise that there is an obligation to archive study-related documents at the end of the study (as such end is defined within this protocol). The CI confirms that she will archive the study master file at UCL for the period stipulated in the protocol and in line with all relevant legal and statutory requirements.

19 PUBLICATION AND DISSEMINATION POLICY

We will disseminate findings via academic journals, conferences, to research participants and via social media and relevant websites (e.g. Alzheimer's Society, National Council for Palliative Care, Marie Curie, Cruse Bereavement Care and carer support agencies). Admiral Nurses on the research team will help dissemination of the resource into their practice. The project's steering group will provide further guidance on dissemination. A half day forum will be held at the end of the study to promote the study findings to members of the Steering Group, study participants and interested stakeholders. Study participants and recruiting agencies will also receive a lay summary of the key findings. A publication plan has been developed that defines authorship and an outline for planned publications arising from the fellowship.

21 LIST OF APPENDICES

1. Case report form – Quantitative interview
2. Pre-interview questionnaire - Health Literacy Questionnaire
3. Semi-Structured Interview guide
4. Letter of invitation distributed by recruiting agencies with expression of interest form
5. Flyer advertising for participants
6. Participant information sheet
7. Cover letter for posted Participant Information Sheet
8. Consent form
